## **Secondary Objectives:**

- To evaluate the therapeutic cure rate of 5% Monolaurin Vaginal Gel compared to Vehicle Placebo Gel at Visits 2 and 3.
- To evaluate the clinical cure rate of 5% Monolaurin Vaginal Gel compared to Vehicle Placebo Gel at Visit 3.
- To evaluate the changes in Nugent's criteria of vaginal bacterial flora at Visits 2 and 3.

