## Nugent criteria

In 1991, Nugent *et al.* described a Gram stain scoring system of vaginal smears to diagnose BV [11]. The Nugent score is calculated by assessing for the presence of large Gram-positive rods (*Lactobacillus* morphotypes), small Gram-variable rods (*G. vaginalis* morphotypes), and curved Gram-variable rods (*Mobiluncus spp.* morphotypes). The Nugent score can range from 0 to 10. A score of 7 to 10 is consistent with BV while 4-6 is considered intermediate and 0-3 is negative for BV. Compared to the Amsel criteria, the Nugent score allows for assessment of alteration in vaginal flora as a continuum rather than a dichotomy.

In the research setting, the Nugent Score is considered the gold standard method for diagnosis of BV [12]). Scoring is as follows:

Table 1: Laboratory examination of vaginal smears and the determination of the Nugent Score

N Score = The sum of the scores for each bacterial morphotype listed below. (Note: Number of Organisms seen/high power field as determined by averaging a representative field by two independent evaluators)

Lactobacilli	SCORE	Gardnerella, Bacteroides	SCORE	Curved gram-negative bacilli	SCORE	Sum= *N SCORE
≥30	0	0	0	0	0	0
<30-5	1	<1	1	<1	1	3
<5-1	2	1 to <5	2	1 to <5	1	5
<1	3	5 to <30	3	5 to <30	2	8
0	4	≥30	4	≥30	2	10

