# 3.2.2. Efficacy Outcomes

# 3.2.2.1. Primary and Secondary Efficacy Outcomes

- Primary Efficacy Outcome Proportion of subjects with clinical cure in each study arm at Visit 2 (Day 8-15).
- Secondary Efficacy Outcomes
  - Proportion of subjects with therapeutic cure in each study arm at Visit 2 (Day 8-15) and at Visit 3 (Day 22-31).
  - Proportion of subjects with Nugent score of 3 or less (negative for BV) and 4-6 (intermediate) in each study arm at Visit 2 (Day 8-15) and at Visit 3 (Day 22-31).
  - Proportion of subjects with clinical cure in each study arm at Visit 3 (Day 22-31).

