#### 11.7.2. Efficacy Analyses

#### 11.7.2.1. Overview of Efficacy Analyses

#### 11.7.2.1.1. Analyses of Primary and Secondary Efficacy Outcomes

• Primary Efficacy Outcome – the proportion of subjects with clinical cure in each study arm at Visit 2 (Day 8-15).

A test of hypothesis for the primary efficacy outcome will be conducted in the mITT efficacy analysis population, and repeated as a secondary analysis in the PP efficacy analysis population, Evaluable efficacy analysis population, and Intent-to-Treat efficacy analysis population. Fisher's exact test at the 5% two-sided level of significance level will be used without adjustment for multiplicity. The point estimates for the arm-specific proportions and difference in proportions as well as corresponding 95% confidence intervals will be reported.

- Secondary Efficacy Outcomes
  - Proportion of subjects with therapeutic cure in each study arm at Visit 2 (Day 8-15) and at Visit 3 (Day 22-31).
  - Proportion of subjects with clinical cure in each study arm by Visit 3 (Day 22-31)
  - Proportion of subjects with Nugent score of 3 or less (negative for BV) and 4-6 (intermediate) in each study arm at Visit 2 (Day 8-15) and at Visit 3 (Day 22-31)

The analyses of the secondary efficacy outcomes will be conducted in the mITT efficacy analysis population and repeated in the PP efficacy analysis population, Evaluable efficacy analysis population and Intent-to-Treat efficacy analysis population. The point estimates for the armspecific proportions and difference in proportions as well as corresponding 95% confidence intervals will be reported.

Additional descriptive analyses of the primary and secondary efficacy outcomes will be performed including tabular and graphical displays of the data, reporting outcomes overall and separately by treatment arm.

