Tables 38-41 presents the number and proportion of subjects with Nugent scores falling in negative BV (3 or less), intermediate (4-6), and BV (7-10) range by analysis population, study visit, and site. The 95% Wilson confidence intervals for the proportion of subjects falling in each category will also be presented. **Tables 42-43** presents the proportion of subjects with Nugent score of 3 or less (negative for BV), 4-6 (intermediate), and 7-10 (positive for BV) in each treatment group at Visit 1, at Visit 2 (Day 8-15) and at Visit 3 (Day 22-31). The number and proportion of subjects with Nugent scores falling in negative, intermediate, and BV range is presented by analysis population, study visit, and treatment group. The 95% Wilson confidence intervals will also be presented. Mean Nugent scores will also be presented by analysis population, study visit, and treatment group in **Table 44.** A subject listing of Nugent scores and bacterial morphotypes will be presented in **Listing 23**. Raw Nugent scores are displayed graphically by visit, treatment group, and analysis population in **Figures 2-5**. Categorical and Continuous Nugent Score characteristics are presented by study visit, clinical cure status, and treatment group for subjects in the ITT population in **Tables 45 and 46**. See Section 6.1 for pseudocode to use in calculating the 95% CIs.

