	Standard Deviation of Mean Change from Visit 1		x.xx	X.XX		X.XX	x.xx		X.XX	x.xx
	Mean	x.xx	x.xx	X.XX	X.XX	X.XX	x.xx	x.xx	X.XX	x.xx
mITT	Standard Deviation of Mean	x.xx	x.xx	X.XX	X.XX	X.XX	x.xx	x.xx	X.XX	x.xx
111111	Mean Change from Visit 1		x.xx	X.XX		X.XX	x.xx		X.XX	x.xx
	Standard Deviation of Mean Change from Visit 1		x.xx	X.XX		X.XX	x.xx		X.XX	x.xx
	Mean	x.xx	x.xx	X.XX	X.XX	X.XX	x.xx	x.xx	X.XX	x.xx
Evoluable	Standard Deviation of Mean	x.xx	x.xx	X.XX	X.XX	X.XX	x.xx	x.xx	X.XX	x.xx
Evaluation	Mean Change from Visit 1		x.xx	X.XX		X.XX	X.XX		X.XX	X.XX
	Standard Deviation of Mean Change from Visit 1		x.xx	x.xx		x.xx	x.xx		x.xx	x.xx
	Mean	x.xx	x.xx	x.xx	x.xx	x.xx	x.xx	x.xx	x.xx	x.xx
DD	Standard Deviation of Mean	x.xx	x.xx	X.XX	X.XX	X.XX	x.xx	x.xx	X.XX	x.xx
I F	Mean Change from Visit 1		x.xx	X.XX		x.xx	X.XX		x.xx	x.xx
	Standard Deviation of Mean Change from Visit 1		X.XX	X.XX		X.XX	X.XX		X.XX	X.XX

Table 44: Continuous Nugent Score Characteristics by Study Visit, Analysis Population, and Treatment Group

			5% M	lonolaı (1	urin Va N=X)	ginal G	el			Pla (cebo Ge N=X)	1				All (N	Subject = xxx)	5	
Visit	Nugent Score Category	Cli C (N	nical ure = X)	Cli Fai (N	nical ilure = X)	ľ Eva (N	Not luable = X)	Cli C (N	nical ure = X)	Cli Fa (N	nical ilure = X)	N Eval (N	Not luable = X)	Cli C (N	nical ure = X)	Cli Fa (N	inical ilure = X)	I Eva (N	Not luable = X)
		n	%	n	%	n	%	n	%	n	%	n	%	n	%	n	%	n	%
Visit 2	0-3 (Normal)	х	X	х	Х	X	х	х	Х	х	X	х	X	Х	х	х	X	X	Х
Test of Cure	4-6 (Intermediate)	х	X	х	Х	X	х	х	Х	х	X	х	X	Х	х	х	X	X	Х
	7-10 (BV)	х	X	х	Х	X	х	х	Х	х	X	х	X	Х	х	х	X	X	Х
	0-3 (Normal)	х	X	х	Х	X	х	х	Х	х	X	х	X	Х	х	х	X	X	Х
Visit 3	4-6 (Intermediate)	х	Х	х	Х	х	х	х	Х	х	X	х	Х	Х	х	х	х	х	Х
	7-10 (BV)	Х	X	Х	х	х	х	х	Х	х	X	х	X	Х	х	х	x	х	х

Table 45: Nugent Scores by Category, Study Visit, Clinical Cure Status, and Treatment Group -ITT Population

Note: Denominator for percentages is the number of subjects in the ITT population for each treatment group.

		5% M	onolaurin Vaş (N=X)	ginal Gel		Placebo Gel (N=X)	l		All Subjects (N = X)	i
Study Visit	Statistic	Clinical Cure (N = X)	Clinical Failure (N = X)	Not Evaluable (N = X)	Clinical Cure (N = X)	Clinical Failure (N = X)	Not Evaluable (N = X)	Clinical Cure (N = X)	Clinical Failure (N = X)	Not Evaluable (N = X)
	Mean	X.XX	X.XX	X.XX	X.XX	X.XX	X.XX	X.XX	X.XX	X.XX
Visit 2 Test of	Standard Deviation of Mean	X.XX	X.XX	X.XX	X.XX	X.XX	X.XX	X.XX	X.XX	X.XX
Cure	Mean Change from Visit 1		X.XX	X.XX		X.XX	X.XX		X.XX	X.XX

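### The secondary objective is change in Nugent's criteria, but SAP Tables 42-44 give no between-arm difference or interval for any Nugent result, including the band difference that Protocol 11.7.2.1.1 requires

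*Protocol*

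**What the plan says.** Protocol 3.1 and SAP 3.1 set the objective: "To evaluate the changes in Nugent's criteria of vaginal bacterial flora at Visits 2 and 3". The outcome attached to it in Protocol 3.2.2.1 and SAP 3.2.2 is "Proportion of subjects with Nugent score of 3 or less (negative for BV) and 4-6 (intermediate) in each study arm" at Visit 2 and at Visit 3. Protocol 2.1, on the Nugent criteria, gives the scale's advantage over Amsel: "the Nugent score allows for assessment of alteration in vaginal flora as a continuum rather than a dichotomy". Protocol 8.2.2 has a slide from every subject at Visits 1, 2 and 3 scored centrally from 0 to 10.

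Protocol 11.7.2.1.1 lists the Nugent proportions among the secondary outcomes. It uses the same sentence for the primary and the secondary outcomes: "The point estimates for the arm-specific proportions and difference in proportions as well as corresponding 95% confidence intervals will be reported".

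SAP 8.2 then says of Tables 42-43: "The number and proportion of subjects with Nugent scores falling in negative, intermediate, and BV range is presented by analysis population, study visit". The breakdown is also by arm, with a Wilson interval for each proportion. The shells give the gel arm and the placebo arm separate tables. For the score, "Mean Nugent scores will also be presented by analysis population, study visit, and treatment group in" Table 44, whose shell adds mean change from Visit 1 and a row labelled "Standard Deviation of Mean Change from Visit 1" for each arm. Lastly, "Raw Nugent scores are displayed graphically by visit, treatment group, and analysis population in" Figures 2-5.

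**The concern.** Change within an arm cannot be credited to the drug. Women on vehicle may improve too: the pilot study in Protocol 2.1.1 reported a significant fall in *Gardnerella* counts on the control gel. What this objective needs from a randomised trial is therefore the contrast between arms, with a measure of its uncertainty. The SAP supplies that contrast for clinical and therapeutic cure but not for Nugent.

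The bands are also an incomplete measure of change. The mITT admits women with a Visit 1 score of 4 or more, so the 4-6 band at follow-up mixes women who improved from 7-10 with women who were already at 4-6. A shift inside a band does not move the band proportions at all. With about 60 vs 30 women, a graded effect on flora could be displayed yet never estimated.

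**Working it through.** **1. What each planned table delivers**

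| Result | SAP table | Between-arm difference | 95% CI for it |
|---|---|---|---|
| Clinical cure, Visit 3 | 30 | yes | yes |
| Therapeutic cure, Visits 2 and 3 | 31-32 | yes | yes |
| Nugent bands | 42-43 | no | no |
| Nugent score and change | 44 | no | no |

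Nugent is the only secondary efficacy outcome without a between-arm estimate.

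**2. The plan's own power figure.** Protocol Table 4 (60 vs 30, two-sided 5% Fisher) is the only power figure, and none is given for Nugent. Power is the sum, over all pairs (x, y) with Fisher p ≤ .05, of Bin(x; 60, p₁) × Bin(y; 30, p₀). Stated against recomputed values, placebo first:
- .10 vs .40: .85 against .869
- .20 vs .50: .78 against .783
- .30 vs .60: .76 against .765

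Of 121 cells, 115 agree within 2 points. The other six are stated 2-4 points low, and none crosses .80. For 80% power a band outcome needs a difference of about 24-32 points (for example .05 to .29, or .20 to .51).

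**3. What the score could deliver.** The SD of change is not in the documents, so a range of 1.5 to 3.5 points is assumed. SE = SD × √(1/60 + 1/30) = 0.2236 × SD.
- 95% half-width = 1.96 × 0.2236 × SD: 0.66 points (SD 1.5), 1.10 (SD 2.5), 1.53 (SD 3.5).
- Difference detectable with 80% power = 2.80 × 0.2236 × SD: 0.94, 1.57 and 2.19 points.

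**4. Limiting case.** If every woman on gel went from 10 to 8 and none on vehicle changed, both arms would have 100% in the 7-10 band, at any sample size. Table 44 would show mean changes of -2 and 0.

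**5. Simulation at 60 vs 30.** Assumed inputs: Visit 1 scores 4-10, mostly 7-10; Visit 2 SD 2.5; slope .5 on the Visit 1 score; the same extra fall for every woman on gel. The figures are shares of trials in which zero is excluded. Ranges run over different assumed Visit 1 mixes. A score of 6 or less is the complement of the 7-10 band.

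| Extra fall | 0-3 band | 6 or less | Unadjusted change | ANCOVA |
|---|---|---|---|---|
| 1 point | 16-18% | 27-29% | 38% | 40-41% |
| 1.5 points | 36-43% | 51-54% | 70% | 74-75% |
| 2 points | 65-71% | 76-77% | 92% | 93-94% |

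With no effect, the 0-3 band excludes zero in 4% and ANCOVA in 5%. At 1.5 points, moving from the 0-3 band to the continuous contrast gains 27-34 points (70 - 43 to 70 - 36). Baseline adjustment adds a further 4-5.

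**6. Sensitivity to the assumptions.** A second model used integer scores, SD 1.5 or 2.5, all women starting at 7-10 or 20% starting at 4-6, and Fisher's test on the bands. For a 1.5-point shift it gives 0-29% for 0-3, 40-81% for 6 or less, and 70-99% for change or ANCOVA. If response is all-or-none the advantage disappears: for 10% vs 30% normalising, 56% (band) vs 52% (ANCOVA); for 20% vs 45%, 67% vs 59%.

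**The case against.** Several stronger readings are tempting, and the documents do not support them.

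- **The trial discards the Visit 1 score, or a shift below a cut-off is undetectable.** Table 44 reports mean change from Visit 1 by arm, and Figures 2-5 plot the raw scores. A reader could subtract the two mean changes and build an interval from the SDs and Ns, taking the SD row as the SD of individual changes, which its label leaves unclear. What is missing is a planned estimate and interval.
- **The bands say nothing about change.** In the mITT every woman starts at 4 or above, so a later score of 0-3 is a move from abnormal to normal. A fall from 8 to 5 crosses the 6/7 cut-off and appears in the 4-6 band.
- **Using bands halves the chance of seeing an effect.** That compares the weakest band with ANCOVA under a uniform shift. Against 6 or less the gap is smaller, and under all-or-none response it vanishes.

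Two defences remain. First, unlike the other two secondary objectives, this one does not mention the vehicle comparison, so change by arm arguably satisfies its wording. But Protocol 11.7.2.1.1 requires a difference between arms for its outcome. Second, SAP 6.1 and 8 say in general terms that intervals for differences in proportions will be computed for efficacy variables. That fixes the method, but neither SAP 8.2 nor the shells of Tables 42-43 apply it to Nugent.

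It is also true that no secondary efficacy outcome has a planned test and that the sample size is described as ad hoc. The simulated shares are therefore a guide to how informative each interval would be. They do not show a failed power target.

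**Conclusion.** The point holds as a gap in estimation. SAP 8.2 omits a difference that the protocol requires for the Nugent bands, and it offers no between-arm contrast for the score, although the objective is change and the data are collected. The omission of the band difference is a plain mismatch between the two documents and rests on no assumption.

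The value of the added score contrast does rest on assumptions, since neither an SD nor a response pattern is given. It is material if the effect is a graded shift of about 1 to 2 points, and nil or slightly negative if women either normalise or do not respond. Most of the gain comes from estimating the difference on the 0-10 scale, and little from adjusting for Visit 1. The score contrast should therefore supplement the bands and not replace them. The primary analysis and the sample size are unaffected.

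**What to change.** In SAP 8.2 and the Table 44 shell, add the between-arm difference in Nugent score at Visit 2 and at Visit 3, adjusted for the Visit 1 score by ANCOVA, with a 95% CI in the mITT. Because the score is ordinal, add a rank-based check, such as a Wilcoxon rank-sum comparison of change with the Hodges-Lehmann shift, pooled across sites as SAP 6.7 provides. Name this as the analysis of the change objective. State the number of women contributing, because SAP 6.5 covers missing cure status and not missing scores. State also how Visit 3 scores taken after other BV treatment are counted.

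In Tables 42-43, add the between-arm difference in each band proportion with its 95% CI, as Protocol 11.7.2.1.1 requires. The code in SAP 6.1.1 already produces that interval. Keep the bands as the named outcome.

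The cost is a few rows in existing tables, with no new data. The downside is a few more secondary estimates without multiplicity adjustment, and an ordinal score treated as numeric, which the rank-based check addresses.

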## **Exploratory Objectives:**

- To evaluate the clinical and therapeutic cure rates of 5% Monolaurin Vaginal Gel compared to Vehicle Placebo Gel for each subgroup (first episode BV and recurrent BV) at Visits 2 and 3.
- To evaluate quantitative changes in selected bacterial species at Visits 2 and 3.
- To evaluate the quantitative changes of Candida spp (in subjects with *Candida spp*. identified at screening) at Visits 2 and 3.

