# 3.2.2.2. Exploratory Efficacy Outcomes

- Proportion of subjects with clinical cure in each study arm by subgroup (first time or recurrent infection) by Visit 2 (Day 8-15) and by Visit 3 (Day 22-31).
- Proportion of subjects with therapeutic cure in each study arm by subgroup (first time or recurrent infection) by Visit 2 (Day 8-15) and by Visit 3 (Day 22-31).
- Mean count of *Lactobacillus spp.*, *Gardnerella spp.*, and *Mobiluncus spp.*, respectively, in each study arm at baseline, Visit 2 (Day 8-15) and at Visit 3 (Day 22-31).
- Mean fungal colony count in vaginal secretions in each study arm at baseline, at Visit 2 (Day 8-15) and at Visit 3 (Day 22-31).

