#### 5.3.1. Randomization Procedures

Subjects will be randomly assigned to active drug or placebo in a 2:1 ratio. Subjects will be stratified by clinical site.

The list of randomized treatment assignments will be prepared by statisticians at the Emmes Corporation and included in the enrollment module of the Emmes Corporation's Internet Data Entry System (IDES). IDES will assign each volunteer a treatment code from the list after demographic and eligibility data have been entered into the system. A designated individual at each site will be provided with a treatment key, which links the treatment code to the actual treatment assignment, which will be kept in a secure place.

Instructions for use of the enrollment module are included in the IDES User's Guide. Manual back-up randomization procedures are provided in the Manual of Procedures (MOP) for use in the event that the site temporarily loses access to the Internet or the online enrollment system is unavailable.

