6.4. Covariates and Subgroups

Clinical and therapeutic cure will be analyzed by subgroup. Subgroups will be defined by first time or recurrent BV infection as defined in Section 3.3. Additionally, subjects with *Candida spp.* identified at screening will be analyzed to evaluate quantitative changes of *Candida spp.* See Section 8.3 for more details on the exploratory efficacy analyses.

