8.1. Primary Efficacy Analysis

The primary efficacy endpoint is the proportion of subjects with clinical cure in each study arm at Visit 2 (Day 8-15), TOC.

A test of hypothesis comparing the proportion of subjects who achieve clinical cure at the Test of Cure Visit, Visit 2 (Day 8-15), will be conducted in the mITT population using the randomized treatment, and repeated as a secondary analysis using the actual treatment received in the PP population and the Evaluable analysis population, and using the randomized treatment in the Intent-to-Treat population. The null hypothesis for each comparison is that there is no difference in proportions of clinical cure between treatment groups, with a two-sided alternative that considers the possibility of a difference in either direction. Fisher's exact test at the 5% two-sided level of significance will be used without adjustment for multiplicity. The number of subjects, the proportion of subjects who achieved clinical cure (clinical cure will be presented for each analysis population and treatment group. In addition, the difference in proportions between the 5% Monolaurin Vaginal Gel arm and the Placebo gel arm and 95% Wilson confidence intervals will be presented. See **Table 29**. See Section 6.1 for pseudocode to fit the above analyses.

A subject listing of individual Amsel criteria will be provided in Listing 22. A summary of Amsel criteria is provided for subjects by visit and site in Table 33. The number of Amsel criteria present (0,1,2,3,4), pH (> 4.5, \leq 4.5), Clue cells (\geq 20%, < 20%), Amine ("whiff") test on KOH wet mount (Positive, Negative), and discharge (yes/no) will be summarized. A summary of Amsel criteria is provided for subjects by visit and treatment group for each analysis population in Tables 34-37. Individual efficacy response data is presented in Listing 10. Reasons for clinical failure are provided in Listing 24.

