8.3. Exploratory Efficacy Analyses

Exploratory efficacy analyses will be performed in the mITT, ITT, Evaluable and PP populations. The mITT and ITT populations will be summarized by randomized treatment and the Evaluable and PP populations will be summarized by actual treatment received.

The first exploratory efficacy endpoint is the proportion of subjects with clinical cure in each treatment group by subgroup (first time or recurrent infection) at the Test of Cure Visit, Visit 2 (Day 8-15) and at Visit 3 (Day 22-31). The number of subjects, the proportion of subjects who achieved clinical cure (clinical cure rate), and the 95% Wilson confidence interval for the proportion of subjects achieving clinical cure will be presented for each analysis population, treatment group, and infection type (first time or recurrent). In addition, the difference in proportions between the 5% Monolaurin Vaginal Gel arm and the Placebo gel arm and 95% Wilson confidence intervals will be presented. See **Tables 47-50**. A listing of subjects BV infection status (first time or recurrent) will be provided in **Listing 25**. See Section 6.1 for pseudocode to use in calculating the 95% CIs.

The second exploratory efficacy endpoint is the proportion of subjects with therapeutic cure in each study arm by subgroup (first time or recurrent infection) at the Test of Cure Visit, Visit 2 (Day 8-15) and at Visit 3 (Day 22-31). The number of subjects, the proportion of subjects who achieved therapeutic cure (therapeutic cure rate), and the 95% Wilson confidence interval for the proportion of subjects achieving therapeutic cure will be presented for each analysis population, treatment group, and infection type (first time or recurrent). In addition, the difference in proportions between the 5% Monolaurin Vaginal Gel arm and the Placebo gel arm and 95% Wilson confidence intervals will be presented. See **Tables 51-54**.

The third exploratory efficacy endpoint is the mean count of *Lactobacillus spp.*, *Gardnerella spp.*, and *Mobiluncus spp.*, respectively, in each treatment group at Visit 1, at Visit 2 (Day 8-15) and at Visit 3 (Day 22-31). Mean count and standard deviation of each specimen type will be presented by study visit, analysis population, and treatment group. Additionally, mean change from baseline and corresponding standard deviation will be presented for Visit 2 and Visit 3. See **Tables 57-60**.

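### First-time and recurrent BV are analysed only as separate arm differences; no estimate of how the two effects differ is planned (minor, exploratory)

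*Protocol*

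**What the plan says.** Protocol 3.1 lists, as exploratory, "To evaluate the clinical and therapeutic cure rates of 5% Monolaurin Vaginal Gel compared to Vehicle Placebo Gel for each subgroup" at Visits 2 and 3. Protocol 11.7.2.1.2 leaves the analysis to the SAP.

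SAP 6.4 says "Clinical and therapeutic cure will be analyzed by subgroup". SAP 3.3.5 and 3.3.6 define the factor by the number of episodes in the previous 12 months, counting the current one: one episode is first-time, two or more is recurrent. For each subgroup, SAP 8.3 gives the cure rate with its interval and adds that "the difference in proportions between the 5% Monolaurin Vaginal Gel arm and the Placebo gel arm and 95% Wilson confidence intervals will be presented". SAP 6.1.1 notes that its code for this interval produces Newcombe limits.

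The subgroups are placed in paired tables: 47 and 48, 49 and 50, 51 and 52, 53 and 54. The shells have no p-value column and no row that compares the subgroups. Neither document contains an interaction term, a difference of differences or any other measure of heterogeneity.

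**The concern.** Splitting the arm comparison by BV history invites the question of whether the gel works differently in the two groups. The quantity that answers it is the difference between the two arm differences, and the plan does not produce it. What remains is to see whether one interval excludes zero while the other does not.

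That comparison misleads because each subgroup is much smaller than the trial. A subgroup interval can include zero through lack of numbers alone, even when the effect is identical in both groups. A reader could then conclude that the gel helps women with first-time BV but not those with recurrent BV, or the reverse, without evidence of a difference. Nothing in SAP 6.4, 6.8 or 8.3 warns against this.

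**Working it through.** **Inputs from the documents.** The mITT target is 90, split 60 and 30 in the power table (Protocol 11.5). Allocation is 2:1 and is stratified by site only (Protocol 5.3.1). The interval is Newcombe's (SAP 6.1.1).

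**Assumptions.** The documents give no design effect and no expected subgroup split; the power table is only a grid of rates. I took the same true rates in both subgroups, a 2:1 ratio within each, and subgroup shares of 50/50, 67/33 and 70/30.

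**The plan's own figure first.** Exact Fisher power at 60 and 30, two-sided 0.05, summed over all binomial outcomes:
- .20 vs .50: .783 (stated .78)
- .30 vs .60: .765 (stated .76)
- .40 vs .70: .760 (stated .76)

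With the same enumeration, the probability that the overall Newcombe interval excludes zero is .817, .773 and .795.

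**Formula for the subgroups.** Let a and b be the probabilities that each subgroup's Newcombe interval lies wholly above zero. Each is the sum of the binomial probabilities of the outcomes for which this is so. The subgroups are independent, so

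P(exactly one) = a(1 − b) + b(1 − a).

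**Placebo .20, gel .50:**
- Even split (30/15 and 30/15): a = b = .496. Exactly one: 2 × .496 × .504 = .500. Both: .246. Neither: .254.
- 67/33 (40/20 and 20/10): a = .634, b = .347. Exactly one: .634 × .653 + .347 × .366 = .541.
- 70/30 (42/21 and 18/9): a = .674, b = .342. Exactly one: .674 × .658 + .342 × .326 = .555.

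Over the same splits, .30 vs .60 gives .498 to .553 and .40 vs .70 gives .500 to .543.

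**Other effect sizes, same splits:**

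| True effect | Placebo/gel | Exactly one excludes zero | Likeliest display |
|---|---|---|---|
| 10 points | .20/.30 | .15-.16 | neither |
| 20 points | .20/.40, .30/.50 | .36-.40 | neither (.54-.59) |
| 30 points | .20/.50, .30/.60, .40/.70 | .50-.56 | exactly one |
| 40 points | .20/.60, .30/.70 | .38-.46 | both (.49-.55) |

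At a placebo rate of .40, the same enumeration gives .15-.19 at 10 points, .36-.41 at 20 and .34-.43 at 40. With no effect and both rates at .20, it gives about .03.

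**The missing contrast.** Take 15/30 vs 3/15 in each subgroup. Each arm difference is .300, with Newcombe limits −.003 and .512, so the distances to the limits are .303 and .212. The contrast is 0. Combining the limits gives a half-width of √(.303² + .212²) = √(.0918 + .0452) = .370.

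The large-sample formula gives a similar value: 1.96 × √[2 × (.5 × .5/30 + .2 × .8/15)] = 1.96 × .195 = .382.

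**The case against.** The strongest reply is that the plan does not make the inference that I warn against. The objective asks for rates in each subgroup and does not ask whether the effects differ. Protocol 11.4 limits formal testing to three hypotheses, none of them in a subgroup. The shell for the primary result (SAP Table 29) has a p-value column and the subgroup shells do not. No rule declares the gel effective in one subgroup and not the other, and no passage ties the subgroup results to a later decision. All of this stands, and it is why the point is minor. It does not close the gap, because a 95% interval that excludes zero is easily read as a test.

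Three stronger readings are tempting, and the documents do not support them:
- **About half of all trials would mislead whenever the effects are identical.** This holds only near a 30-point effect, and the documents state no effect.
- **A split result is the likeliest display under any real, uniform benefit.** At 20 points, neither interval excluding zero is likelier. At 40 points, both excluding zero is likelier.
- **Endpoints, visits and populations multiply into 16 separate chances of error.** The Evaluable set is a subset of the mITT, and therapeutic cure requires clinical cure, so the tables overlap heavily.

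It is also fair to say that the added row will rarely separate the subgroups. Its use is to show how little this trial can say on the question.

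**Conclusion.** The gap is real: SAP 8.3 gives separate within-subgroup arm differences and no estimate of how they differ. Under an identical 30-point effect, with overall intervals that would exclude zero in 77-82% of trials, exactly one subgroup interval would do so in about 50-56%. This rests on 60 and 30 women in the mITT arms, 2:1 allocation within each subgroup, subgroup shares between 30% and 70%, and placebo rates of .20 to .40. The effect, shares and rates are my assumptions. The risk is smaller at effects of 10, 20 or 40 points and close to nil with no effect. The objective is exploratory and the plan draws no subgroup conclusion, so this is a cheap improvement and not a flaw in the primary analysis.

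**What to change.** In SAP 8.3, show first-time and recurrent BV side by side for each endpoint and visit. In the mITT, add one row with the first-time minus recurrent difference in arm differences, on the risk-difference scale. Obtain its 95% interval by combining the Newcombe limits already computed for the two subgroups. Label the row exploratory, and state that any claim of a differing effect is read from it alone.

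The cost is one row per pair of tables, with no new data, visits or tests. The drawback is a wide interval, about ±37 points in the worked case, so the subgroup results will look less definite.
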